## Clinic Identification, Recruitment & Assignment

Clinics will be included in the recruitment pool for this study if they (1) provide primary care to adults with high CVD risk annually, and (2) have been using OCHIN's EHR for at least 18 months. Once all clinics have been recruited as outlined in Section 5.e., they will be assigned to either arm 1 or arm 2. Clinics were grouped based on the baseline number of encounters each service area had, percent of patients with hypertension, and percent of patients who use tobacco. Five randomly generated groupings were created and the grouping that created the most even distribution across both Arms was then selected to assign service areas and the clinics within each service area to an Arm.

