## **Primary Outcome Measures**

- **Study Aim 1:** Compare patients' change in reversible risk in the Arm 1 vs. Arm 2 CHCs (in months 18-35)
- **Study Aim 2**: Assess whether the revised implementation support materials expedite CDS adoption
- **Study Aim 3:** Use mixed methods to identify multi-level barriers / facilitators to adoption of the CDS tool

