#### **Quantitative Data**

To be included in Aim 1 analyses a patient must have at least one visit in the 6 months after the Arm 1 implementation date at an Arm 1 or Arm 2 CHC and at least one additional visit at a study clinic in the 12-month post-index visit period. The first visit is referred to as the index visit. We will describe those who had inadequate follow-up data (did not have at least one additional visit in the post-index period). For each study subject, CVD risk score / risk factor management status will be calculated at index visit and each encounter during follow-up. While the tool can be run for patients of any age, we will restrict our analyses to patients 40-75 years of age.

We will test for between-group differences in baseline characteristics such as age, sex, race and ethnicity, insurance type, visit count, and health status using chi-square, t-test, and nonparametric Wilcoxon rank-sum tests as appropriate. We will also test for association between baseline characteristics and our outcomes of interest. We will examine the number of patients seen in each service area and clinic and each Arm and compare the characteristics of Arm 1 patients for whom the tool was used to those in Arm 1 for whom the tool was not used and to Arm 2 patients. Because the two arms were selected based on clinic size, percent of patients with a diagnosis for hypertension and the percent of patients that use tobacco, we anticipate there will be differences between the two groups resulting in the need to adjust for these differences. We will also examine characteristics at the service area and clinic-level in Arm 1 for whom the tool was used compared to Arm 1 service areas / clinics for whom the tool was not used and Arm 2 service areas / clinics.

Unadjusted trends in the monthly use and view rates for each of the study CHCs will be explored with use rates defined as: the number of encounters where CV Wizard was printed / number of targeted encounters with high-CVD risk patients per month and view rates defined as the number of encounters where CV Wizard was viewed / number of targeted encounters with high-CV risk patients per month.

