We will also examine overall rates of each of the impact outcomes (BMI in normal range, controlled blood pressure, controlled LDL, controlled HbA1c, and non-smoking status) pre/post tool use to assess any changes in patterns for patients in Arm 1 for whom the tool was used compared to those in Arm 1 for whom the tool was not used as well as to Arm 2 patients. The date the tool was first used for each patient will be assigned as the start of the post-period.

Extent of adoption of a CDS tool like CV Wizard directly impacts its population-level impact. To differentiate between the tool's population level impact versus impact when used, we will conduct intent to treat (ITT) analyses to compare all targeted patients at intervention versus control clinics. We will also conduct effect of treatment on the treated (ETOT; also called per protocol) analyses limited to intervention CHC patients for whom the CV Wizard tool was used (results viewed / printed out) at the index visit, compared to intervention clinic patients for whom it was not used, and separately, to control clinic patients. The ITT analyses test the hypotheses that targeted patients in intervention clinics will have significantly lower CVD risk scores and higher rates of CVD risk factor control, at visits in the year post-index visit period, compared to similar patients in control clinics. The ETOT analyses test the hypotheses that targeted patients in intervention clinics for whom the CV Wizard CDS tool results are viewed and / or printed will have significantly lower CVD risk scores and higher rates of CVD risk factor control, at visits in the year post-index visit period, compared to similar patients in control clinics, and compared to patients in intervention clinics for whom the tool alerted but was ignored at the index visit.

Analyses will be stratified by first-time and repeat patients to see if there is a difference in tool use as well as examine whether the time between visits effects tool use among repeat patients.

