### **Intent to Treat Analysis**

Differences in change in outcomes will assessed using multi-level mixed models. Intra-class correlation coefficients will be obtained at the patient, clinic, and CHC organization levels for each outcome showed that much organization-level variance could be attributed to the clinic level. Thus, clustering was accounted for by random effects for clinic and patient, and a fixed effect for organization. Analyses will adjust for fixed effects: distribution of eligible patients by age, race / ethnicity, gender, rural / urban status, and federal poverty level (FPL) at index visit; number of ambulatory visits during the follow-up period; and time from index to last visit. These variables were selected *a priori* and will be confirmed by descriptive analyses, to determine whether there are significant differences between baseline intervention and control organization and patient characteristics. After checking distributions, negative binomial mixed-models or poisson mixed-model will be used for reversible risk analyses, and linear-mixed models for all other outcomes.

Patients diagnosed with diabetes during the follow-up period will be excluded from reversible risk analyses because diabetes might be diagnosed more often with CDSS use. Presence of diabetes raises reversible risk estimations even if CVD risk factor control was addressed; this exclusion will remove the possibility of confounding based on likelihood on new diabetes diagnosis.

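### The intention-to-treat model for reversible risk leaves its response unstated, does not list index risk as a covariate and specifies no absolute-point effect; index adjustment would bring a modest, conditional gain

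*Combined protocol and SAP*

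**What the plan says.** Section 7.a, Intent to Treat Analysis, sets out the model.

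- **Contrast:** "Differences in change in outcomes will assessed using multi-level mixed models".
- **Covariates:** "Analyses will adjust for fixed effects: distribution of eligible patients by age, race / ethnicity, gender, rural / urban status", followed by federal poverty level at index, the count of follow-up visits and the length of follow-up. Index reversible risk is not listed.
- **Family:** "negative binomial mixed-models or poisson mixed-model will be used for reversible risk analyses". No link, contrast or absolute measure is given.
- **Clustering:** "clustering was accounted for by random effects for clinic and patient, and a fixed effect for organization". The reason given is that much of the organization-level variance belonged to clinics.

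Other sections bear on the same model.

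- Section 6.a, Primary Outcome Measures, defines the Aim 1 outcome as change in reversible risk.
- Section 7.a, Quantitative Data, says "CVD risk score / risk factor management status will be calculated at index visit and each encounter during follow-up". It also says "The ITT analyses test the hypotheses that targeted patients in intervention clinics will have significantly lower CVD risk scores", meaning levels at visits in the year after index.
- Section 7.a, Statistical Power, varies a group-by-time effect and the ICC for 60 clinics of more than 35 patients, and considers differences of 1.5, 2 and 3 absolute points.
- The Effect of Treatment on the Treated section matches on the baseline value of the outcome and uses linear mixed models.
- Section 6.a, Clinic Identification, Recruitment & Assignment, chose a grouping to "assign service areas and the clinics within each service area to an Arm". No section says whether one organization can have service areas in both arms. The intention-to-treat and treated-patient sections speak of intervention and control organizations, which suggests that it cannot.

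**The concern.** The text allows three responses, and each has a cost.

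1. A literal change score does not fit the named families, because Poisson and negative binomial models cannot take negative values and a fall in risk is the hoped-for result.
2. Follow-up scores alone, with a fixed organization effect, leave no information on arm if every organization lies wholly in one arm.
3. Repeated scores with an arm-by-time term can be fitted, but may give up precision that is available from data already in hand.

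Separately, a ratio from a log-link count model cannot be set against the 1.5 to 3 points considered for power unless it is converted. Two analysts could follow the section and report different primary results on different scales.

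**Working it through.** **1. The plan's own figure.** The only numeric power is for Supplement Aim 2b: 6000 per group, difference 5.0, SD 9.1 at both times, correlation 0.2, two-sided alpha 0.05. SD of change = 9.1 x sqrt(2 x 0.8) = 11.51; SE = 11.51 x sqrt(2/6000) = 0.210; 5.0/0.210 = 23.8 standard errors, so power is 100% and the figure reproduces. Aim 1 gives no power, SD, ICC, correlation or number of randomised clusters. All inputs below are therefore assumptions, and the SD of 9.1 is borrowed.

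**2. The three responses.**

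- *Change.* At a mean change of -1.5 points with normal errors, the negative share is Phi(1.5/SD of change). The SD is 11.5, 9.1 or 5.8 at correlation 0.2, 0.5 or 0.8, giving 55%, 57% or 60%.
- *Follow-up level.* With 20 organizations (illustrative), the indicators have rank 20. Adding an arm column leaves the rank at 20 if organizations are nested in arms, so arm cannot be estimated. The rank becomes 21 if organizations are split across arms.
- *Repeated scores.* In a linear model with organization fixed and nested in arms, the arm-by-time estimate equals the change-score estimate (they differ by 2.5e-14). A common-baseline constraint changes nothing: SE 0.592 either way (60 clinics of 35, SD 9.1, clinic ICC 0.05, cluster correlation 0.8, patient correlation 0.2).

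**3. Gain from index adjustment, nested case, random cluster effect.** Let J be the number of clusters, m = N/J, total variance 1, Vc = ICC, Vp = 1 - ICC, c the correlation of cluster effects over time and r the patient correlation. Variance per cluster:

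- change: 2Vc(1-c) + 2Vp(1-r)/m
- patient index only: Vc(1+r²-2rc) + Vp(1-r²)/m
- index plus cluster mean: (B - C²/B)(J-3)/(J-4), with B = Vc + Vp/m and C = cVc + rVp/m

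Example: J = 20, N = 2,100 (60 x 35), m = 105, ICC 0.02, c 0.8, r 0.5, so Vp/m = 0.00933.

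- Change: 0.00800 + 0.00933 = 0.01733.
- Patient index only: 0.00900 + 0.00700 = 0.01600, a fall of 7.7%.
- Index plus cluster mean: B = 0.02933, C = 0.02067, (0.02933 - 0.01456) x 17/16 = 0.01570, a fall of 9.4%.

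Over N = 2,100 or 12,000 and r = 0.2, 0.5 or 0.8, the fall in variance against change for index plus cluster mean is:

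| Clusters | ICC | c | Fall in variance |
|---|---|---|---|
| 10 | 0.01-0.02 | 0.5-0.8 | -5.0% to 18.1% |
| 20 | 0.01-0.02 | 0.5-0.8 | 4.4% to 28.0% |
| 30 | 0.01-0.02 | 0.5-0.8 | 6.5% to 31.2% |
| 10 | 0.01-0.10 | 0.5-0.95 | -14% to 18% |
| 20 | 0.01-0.10 | 0.5-0.95 | -3.5% to 28% |

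A negative fall is a loss. For 20 clusters in the narrower grid, interval width is multiplied by sqrt(1-0.044) = 0.978 to sqrt(1-0.280) = 0.849, so it is 2 to 15% narrower. Patient index alone in that grid runs from -50.5% to 30.4%. The worst case is N = 12,000, ICC 0.02, c 0.8, r 0.2, where it is 0.01597 against 0.01061 for change.

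**4. Other structures.** A three-level simulation (20 organizations x 3 clinics x 35 patients, organization and clinic ICC 0.01 each) gives falls of 1.4 to 26.9% over six settings. A simulation with overdispersed counts (mean 10, 20 clusters of 105) gives 6.7 to 25.1% for the standardised absolute difference. In the setting with SE 0.592 above, making organization random and adjusting for index gives SE 0.527; power at 1.5 points rises from 72% to 81%.

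**5. Scale.** The ratio for a 1.5-point fall is 1 - 1.5/mean: 0.70, 0.85 or 0.925 at assumed means of 5, 10 or 20. One ratio therefore does not fix the absolute effect.

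**The case against.** The strongest reply is that the text, read as a whole, points to repeated scores: scores at index and every encounter, a random patient effect, differences in change, and a group-by-time term in the power section. On that reading the index value is part of the response, and its absence from the covariate list is not in itself a defect. This stands. A reader might infer that the primary analysis cannot be fitted, or that it ignores baseline; the documents support neither. The failure to fit applies to two other readings, one of them only under nesting.

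A reader might also infer that index adjustment helps only if organization becomes random. That holds only when organizations lie wholly within arms, which the documents suggest but do not state. If organizations are split, adjustment helps with organization still fixed: in one setting (organization ICC 0.02, clinic ICC 0.03, c 0.8, r 0.2) the SE is 0.596 for follow-up only, 0.563 for change and 0.495 with index adjustment.

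Three further points stand. The gain rests wholly on assumed inputs. The equality with a change score is shown for a linear model, not for the planned count mixed model. The cluster mean gains less than patient index alone in 12 of the 24 settings of the narrower 20-cluster grid; in the three-level simulation at r 0.8 and c 0.8, the SD of the estimate is 0.379 for change, 0.363 with patient index and 0.376 with the mean added.

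The plan's reason for the fixed effect, that organization variance sits largely at clinic level, concerns where the variance lies. It does not restore an arm effect that nested fixed effects absorb. A ratio can be converted to points, but the plan does not say that it will be.

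**Conclusion.** The point holds in a limited form. The response, the role of index risk and the reporting scale are unspecified for the primary outcome, and the organization term is safe or unsafe depending on a mapping that the documents do not give. The best-fitting reading can be run, but under nesting and a linear model it is only as precise as a change score.

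The precision gain is secondary and conditional. It is worth having with about 20 or more clusters and moderately stable cluster means, and may be nil or negative with about 10 clusters or very stable means. The stronger reason to act is that the primary estimate should not depend on which reading an analyst picks. Confidence is medium, because every Aim 1 variance input is assumed.

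**What to change.** - **(a) Response.** State it as reversible risk at follow-up, and say whether that means the last visit or every visit in the 12 months after index.
- **(b) Index risk.** Adjust for the patient's index reversible risk, with its service-area or clinic mean as a safeguard. A common-baseline constraint is an alternative, but not with nested fixed organization effects, where it gains nothing. Base the index score on data not influenced by the tool, since index visits follow Arm 1 implementation.
- **(c) Organization.** State how organizations and service areas map to arms. If organizations lie within arms, replace the fixed effect with a random organization or service-area effect. If they are split, the fixed effect can stay.
- **(d) Reporting.** Give the adjusted absolute percentage-point difference with its confidence interval, by marginal standardisation if a count family is kept or from a linear mixed model; the family is the sponsor's choice. Use a small-sample correction for the number of randomised clusters.

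The cost is plan wording and a little analysis time. Index scores are already calculated, although one free of the tool's influence may need a check on when its inputs were recorded. The cluster mean uses one cluster-level degree of freedom and sometimes gains less than patient index alone; in return it guards against losses as large as the 50% seen in the narrower 20-cluster grid.

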#### **Secondary Outcome Measures**

- **Reach: Encounters affected** % clinic encounters where CV Wizard suggests running the full risk assessment tool, i.e., identified a target patient.
- Effectiveness (impact): Patient outcomes 10-year pooled ASCVD risk score change in ASCVD risk score from baseline to last visit of study period (American College of Cardiology-ACC/ American Heart Association - AHA) 10-year pooled ASCVD risk score, 40-75 year olds
- Effectiveness (impact): Patient outcomes last BP ≤140/90 Control of individual CVD risk factors: last BP ≤140/90
- Effectiveness (impact): Patient outcomes last A1c≤8 Control of individual CVD risk factors: last A1c≤8
- Effectiveness (impact): Patient outcomes last LDL<100 Control of individual CVD risk factors: last LDL<100
- Effectiveness (impact): Patient outcomes not current smoker Control of individual CVD risk factors: not current smoker
- Effectiveness (impact): Patient outcomes last BMI ≤25 Control of individual CVD risk factors: last BMI≤25
- Adoption: CDS uptake % of encounters where care team member opts to run the CV
   Wizard risk assessment (explored as both view and print rate and just print rate)
- Implementation: User perceptions Perceived ease of use, usefulness, acceptability of CV Wizard; intent to use it.
- Maintenance over time All measures over 2.5 years of follow-up, Arm 1; 1.5 years, Arm 2.

Table 6. Impact and uptake of the CV Wizard system: Quantitative Measures		
Outcomes, per RE-AIM	Measurement	
Reach:	% clinic encounters where CV Wizard suggests running the full risk assessment tool,	
Encounters affected	i.e., identified a target patient	
Effectiveness (impact):	(i) change in ASCVD risk score (reversible risk; ACC/AHA 10-year pooled ASCVD risk	
Patient outcomes	score, 40-75 year olds; Framingham 30-year CVD risk score, 20-39 year olds).	
	(ii) Control of individual CVD risk factors: last BP ≤140/90; last A1c≤8; last LDL<100;	
	not current smoker; last BMI≤25);	
Adoption: CDS uptake	% of encounters where care team member opts to run the CV Wizard risk	
	assessment	
Implementation: User	Perceived ease of use, usefulness, acceptability of CV Wizard; intent to use it; see	
perceptions	3.3.f.ii	
Maintenance over time	All measures over 2.5 years of follow-up, Arm 1; 1.5 years, Arm 2	
Potential covariates	Measurement	
Patient demographic	Age; gender; race / ethnicity; primary language; poverty level; insurance status at	

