#### Statistical Power

To conservatively calculate power for our main outcome (CVD risk score) we estimated 60 clinics with >35 high-CVD risk patients, randomized to two arms; then, using means and standard deviations for this measure from previous studies, we varied effect size associated with the group x time interaction and intraclass correlation. We examined a 1.5%, 2%, 3% greater absolute reduction in risk score over time in intervention vs. control CHCs. Aggressive management can reduce 10-year CVD risk by an absolute 4-5% in high-risk patients in a short time. We do not expect so large an effect and have power to detect smaller effects. **Supplement Addendum (Aim 2b).** This is a 2x2 repeated measures design with two groups of subjects measured at two time points. The primary goal is to compare change across time in group 1 (inperson index encounters) to change across time in group 2 (VC index encounters). A conservative estimate (based on preliminary results from the parent study) of 6000 patients in group 1 and 6000 in group 2 achieve 100% power to detect a difference in mean changes in CVD risk score of 5.0, with a standard deviation of 9.1 at the first time point, a standard deviation of 9.1 at the second time point, and a correlation between measurement pairs of 0.200. The significance level (alpha) is 0.050 using a two-sided, two-sample t-test.

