## b. Potential Benefits to Subjects

### **Overall Benefits**

This study is expected to yield several key benefits. It will determine whether and how clinical decision support (CDS) tools that address multiple aspects of guideline-based CVD prevention and care, have provider- and patient-facing elements (enabling patient engagement), and involve some workflow changes, can and will be adopted by, and will successfully increase rates of guideline-concordant care in CHCs. The use of sophisticated CDS in populations with persistent disparities is a long overdue, critical step towards addressing CVD risk/outcome disparities in socioeconomically vulnerable (i.e., CHC) populations in the US. This study will determine how persistent guideline-to-practice gaps impacting high-risk/prevalence patients can be addressed using targeted, innovative, multi-level, team-based decision support tools. Thus, key benefits include: (1) Collecting, documenting and presenting data on prioritized CVD risk to care teams and patients may result in patients receiving care that ultimately improves their health. This potential benefit will incur no additional clinic visits or costs to patients. (2) The intervention will increase care teams' knowledge about CVD risks that may influence their patients' health. (3) This intervention may bring improvements in EHR functionality

to CHCs that would otherwise not receive them. (4) Because this study develops and tests different ways of presenting CVD risk data in clinic EMRs, it will provide needed information on how prioritized CVD risk data can be used to improve care and services in community health center populations nationwide.

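### The intent-to-treat covariate list includes two measures taken after randomization and omits the three variables used to form the arms

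*Combined protocol and SAP*

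**What the plan says.** All references are to the combined protocol and SAP.

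- **Purpose (7.a, Quantitative Data).** To separate population-level impact from impact when the tool is used, "we will conduct intent to treat (ITT) analyses to compare all targeted patients at intervention versus control clinics".
- **Model (7.a, Intent to Treat Analysis).** Differences in change are assessed with mixed models that have "random effects for clinic and patient, and a fixed effect for organization". Reversible risk gets a Poisson or negative binomial model, and every other outcome a linear one. No equation is given, and no term is named as the arm effect.
- **Covariates (same section).** Five index-visit factors, plus "number of ambulatory visits during the follow-up period; and time from index to last visit".
- **What is compared.** The Aim 1 primary outcome is change in reversible risk. The hypothesis concerns scores and control rates "at visits in the year post-index visit period, compared to similar patients in control clinics". Secondary Outcome Measures has "change in ASCVD risk score from baseline to last visit of study period". Statistical Power varied the "effect size associated with the group x time interaction and intraclass correlation".
- **Data (7.a, Quantitative Data).** Risk is scored at index and at every follow-up encounter. Inclusion requires "at least one additional visit at a study clinic in the 12-month post-index visit period".
- **Allocation (6.a, Clinic Identification, Recruitment & Assignment).** Service areas were allocated using baseline encounter volume, hypertension prevalence and tobacco use, by taking the most even of five random groupings. Quantitative Data expects differences as a result and says they must be adjusted for. None of the three is in the intent-to-treat list.

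**The concern.** An intent-to-treat effect at population level should include whatever the tool does through visit frequency. Follow-up visit count could lie on that path, and the interval to the last visit is likewise observed only after assignment. If the tool changes visit frequency, adjustment can act in two ways. It removes the part of the effect that runs through visits. It also compares unlike patients: if sicker patients visit more, an Arm 1 patient and an Arm 2 patient with equal visit counts differ in severity.

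The plan already accepts that the tool can alter events after randomization. It excludes patients newly diagnosed with diabetes from the reversible-risk analyses because tool use might raise the diagnosis rate. Visit count deserves the same question.

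The second fault is an inconsistency: one section says the allocation variables create a need to adjust, and the section that lists the covariates leaves them out. At stake are the meaning of the arm coefficient for some outcomes and the precision of the comparison.

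**Working it through.** **1. Inputs.** For Aim 1, Statistical Power gives 60 clinics with more than 35 patients each and target differences of 1.5, 2 and 3 points. It gives no SD, intraclass correlation or achieved power, so nothing can be reproduced. The supplement's figure can be. SD of change = 9.1 × √(2 × (1 − 0.2)) = 11.51. SE = 11.51 × √(2/6000) = 0.210. Then 5.0/0.210 = 23.8, so power is 100%, as stated. Only that SD and correlation are borrowed below.

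The rest is assumed. Mean follow-up visits are 4.0 in Arm 2 and 4.8 in Arm 1 (a 20% rise). Visits are 1 plus a Poisson count. The direct arm effect is −1 point. Each visit lowers risk by b points. Severity U (SD 1) multiplies the Poisson rate by exp(0.3U) and raises follow-up risk by g points per SD.

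**2. Which model the text implies.** A signed change score cannot be a Poisson or negative binomial outcome. No baseline outcome value is in the covariate list, so a follow-up-level model would not estimate change. The patient random effect, the score at each encounter and the power section all fit repeated rows with an arm-by-time effect. For the primary outcome that is the natural reading. For the linear outcomes, change from baseline to last visit with one row per patient remains open.

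**3. Arm-by-time, visits as a main effect.** Visit count is constant within a patient, so it drops out of the within-patient change. A Poisson version (risk 5% lower per visit) gives an arm-by-time rate ratio of 0.889 with and without visits.

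**4. Change model.** Through visits, total effect = −1 − 0.8b, against −1 after adjustment: −1.40 for b = 0.5 and −1.80 for b = 1. Through severity, shift = −g × s × 0.8, where s is the within-arm slope of U on visits. Pooled covariance over variance is (0.90 + 1.14)/(3.85 + 5.16) = 0.226, so the shift is −0.36 for g = 2 and −0.72 for g = 4. Simulated arm effects, without / with visit count:

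| Assumption | Change model | Arm-by-time, two times | Arm-by-time, one row per encounter |
|---|---|---|---|
| b = 0.5 | −1.39 / −0.99 | −1.394 / −1.394 | −1.419 / −1.411 |
| b = 1 | −1.81 / −1.00 | −1.805 / −1.805 | −1.851 / −1.835 |
| g = 2 | −0.99 / −1.36 | – | – |
| g = 4 | −1.04 / −1.76 | −1.038 / −1.038 | −1.026 / −1.039 |
| b = 0.5, g = 2 | −1.42 / −1.39 | – | – |

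A model of follow-up rows only behaves like the change model (b = 0.5: −1.397 / −0.985). Adding visits-by-time to the arm-by-time model also brings the shift back (−1.394 to −0.991). At a 10% rise the shifts are about half. With no difference in visits, the two estimates agree to within 0.01.

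A second simulation used 60 clinics of 35 patients, a direct effect of −1.5 and arm differences in visits of about +0.45 or −0.36. The change-model shift ran from −0.28 to +0.27. The arm-by-time shift was 0 with two times and at most 0.002 with all encounters.

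**5. Organization term.** Take 20 organizations, each wholly in one arm. With one row per patient, organization plus arm has rank 20 in 21 columns, so an arm main effect cannot be estimated. With two times, organization, time and arm-by-time have rank 22 of 22, and 25 of 25 with three further time interactions.

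**6. Allocation variables.** Under best-of-five allocation, with assumed strong prediction of change (1 point per SD each), the estimate is −1.50 with or without them. The model SE is 0.76 without and 0.62 with, against actual spreads of 0.65 and 0.61. If they predict level only, there is no gain (0.62 both ways). For a cluster-mean comparison, SE ratio = √{[(1 − ICC)/35 + ICC(1 − R²)] / [(1 − ICC)/35 + ICC]}. For R² of 0.3 and 0.5 this gives 0.960 and 0.932 at ICC 0.01, and 0.898 and 0.822 at ICC 0.05: a reduction of 4% to 18%.

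**The case against.** A reader might infer that visit adjustment biases the primary result. The documents do not support that. The count model, the patient random effect and the power section point to arm-by-time, where the shift is nil or negligible, and the visits-by-time term that would restore it appears nowhere in the plan. No document gives a visit difference. Overall Benefits (10.b) states: "This potential benefit will incur no additional clinic visits or costs to patients". That sentence is about patient burden and does not settle the analysis, but it gives no ground for assuming a rise. These points stand, and they confine the concern to the linear outcomes and to a follow-up-level reading of the hypothesis.

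Visit adjustment also has a plausible purpose, since outcomes are seen only at encounters. That justifies a sensitivity analysis; it does not make the adjusted coefficient a total effect.

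A reader might also infer that omitting the allocation variables biases the comparison. The most even grouping was chosen, and the check found no bias. Table 6 allows for other clinic factors, and the covariate list is to be confirmed by descriptive analyses. But that confirmation concerns baseline differences. It cannot justify a follow-up visit count, and it does not commit the plan to adding the three variables.

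**Conclusion.** The point holds in a limited form.

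- **Primary outcome.** On the arm-by-time reading, visit count as a main effect causes a shift of 0 with two time points and at most about 0.02 points with one row per encounter.
- **Linear outcomes analysed as change, or any follow-up-level model.** The adjusted arm coefficient is not the total effect if visits differ by arm. Direction and size are unknown. The 0.03 to 0.81 points at a 20% rise rest wholly on assumed visit, per-visit and severity effects, and on an SD and correlation taken from the supplement. The bias is zero if visits do not differ.
- **Allocation variables.** Their omission contradicts the plan's own stated need. The expected cost is precision: 4% to 18% of the SE if they explain 30% to 50% of between-cluster variance.

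The plan does not say whether a service area is an organization, so whether an arm main effect can be estimated at all is open.

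**What to change.** In the Intent to Treat Analysis section:

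1. State that the arm effect is the arm-by-time term for every outcome, and state how service areas relate to organizations.
2. Use baseline covariates only in the primary model. If a utilization covariate is wanted, take the prior-year visit count in Table 6. Use elapsed time only as the time axis.
3. Add the three allocation variables at service-area level with time interactions, so that the organization effect does not absorb them.
4. Keep the visit-adjusted model as a labelled sensitivity analysis, stating whether visits interact with time.
5. Report follow-up visits, and the proportion with a return visit, by arm. The return-visit requirement is a separate selection that this fix does not remove. If Arm 1's return rate were 3 to 5 points higher (from an assumed 75% or 85%), the shift would be about 0.02 to 0.11 points, with sign depending on who returns; it is zero if return rates are equal.

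The cost is SAP wording and one extra table. The variables are already held or planned for collection. A few cluster-level degrees of freedom are spent, and any precision from follow-up visit count is lost, though the prior-year count may recover part of it.
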